Profiling the Skin Microbiome in Response to Altreno in Acne Patients

NCT #: 04548349

Document Date: June 15, 2020

Study Design

This is a single-center, prospective study.

Study Population

Up to 60 subjects who meet study inclusion/exclusion criteria will be recruited into the study.

Materials and Methods

We will prospectively recruit healthy controls and acne patients from the BIDMC dermatology clinic as follows:

- **Control Group:** We will recruit up to 20 healthy controls without any skin diseases.
- **Experimental Group:** We will recruit up to 40 patients with acne with severity that warrants initiation of a topical medication and randomize 20 patients into Altreno 0.05% lotion monotherapy (applied once daily) and 20 patients into BPO 2.5% leave-on gel monotherapy (applied once or twice daily as tolerated).

Control Group will undergo skin swab at baseline and approximately 120 days later without any intervention. During the entire study period, the Group will not be allowed to use any antibacterial wash, other than approved OTC cleansers. *If due to the pandemic, subjects cannot return for 2nd visit in 120 days, the subjects will still remain in the study until able to do so.

Experimental Group will undergo skin swab at baseline, as well as clinical scoring of acne. Then, they will be prospectively divided 1 to 1 into Altreno group or BPO group. During the following 90 days, the Group will only be allowed to use either Altreno or BPO. On the second visit (90 days +/- 5 days), their acne will be scored again, and repeat skin swab will be taken. If significant improvement, they will be asked to discontinue the therapy for 30 days. If no significant improvement, they will be instructed to continue the therapy for additional 30 days. On the third visit (120 days +/- 5 days from the first visit), their acne will be scored, and repeat skin swab will be taken. *If due to the pandemic, subjects cannot return for subsequent visits, the subjects will either continue the therapy (or continue without therapy) and remain in the study until able to return for the subsequent visits.

All skin swab samples will be stored at -80 °C until further processing. CoreBiome will receive skin swabs (with subject ID only, no other PHI), they will extract DNA, and perform 16S rRNA gene and/or shotgun metagenomic sequencing. Corebiome will send the BIDMC research team the raw data. The research team will be doing the bioinformatics/analysis, not CoreBiome. If, after sending the skin swabs, subject withdraws, then the PI will ask Corebiome to destroy the sample and they will not perform DNA extraction or 16S rRNA/shotgun metagenomic sequencing.

Control Group:

Procedures and Measurements	Visit 1	Visit 2
Procedures and Measurements	Screening Day 0	Day 120 +/- 5 days
Informed Consent, HIPPA Auth, Photo Release	X	
Review Inclusion/Exclusion Criteria	X	
Review of Demographics	X	
Review of Medical/Surgical Histories	X	X
Review of Current Medications	X	X
Physical Examination of Unaffected Skin	X	X
Regular Photography	X	X
Skin Swabs	X	X
Assess for Adverse Events	X	X

Experimental Group:

Procedures and Measurements	Visit 1	Visit 2	Visit 3
Procedures and Measurements	Screening Day 0	Day 90 +/- 5 days	Day 120 +/- 5 days
Informed Consent, HIPPA Auth, Photo Release	X		
Review of Inclusion/Exclusion Criteria	X		
Review of Demographics	X		
Review of Medical/Surgical Histories	X	X	X
Review of Current Medications	X	X	X
Review of Acne Histories	X		
Review of Past/Current Acne Medications	X		
Physical Examination of Acne Skin	X	X	X
Acne Leeds Score	X	X	X
Acne PGA Score	X	X	X
Regular Photography	X	X	X
Skin Swabs	X	X	X
Assess for Adverse Events	X	X	X

Data Analysis

Primary Study Parameter(s): The primary outcome of this study is assessing for changes in skin microbial composition in acne patients after treatment with Altreno or BPO by specifically comparing their skin microbiomes (1) at baseline, (2) after 3 months of treatment, and (3) 1 month 10 after discontinuation of treatment. Comparisons of species diversity and relative abundance of the identified species will be made across healthy controls, Altreno group, and BPO group.

The raw sequencing data will be first processed into taxonomic features using the standardized DADA2 protocol as implemented in the bioBakery. Then, we will analyze the

three available microbial features (taxa, alpha diversity summary statistics, and community structure via beta diversity) across the three groups defined above.

Secondary Study Parameter(s): The clinical severity will also be correlated to the presence and/or dominance of *P. acnes* and other populations using the following measures:

- **Physician Global Assessment of Acne:** Categorical variable. A chi-square test will be performed for analysis.
- **Leeds Acne Score:** Ordinal variable. A correlation analysis and depending on distribution, one-way ANOVA, a Kruskal Wallis or a Wilcoxon rank sum test will be performed for analysis.

Other Study Parameter(s): Patient characteristics and demographics data will be presented using descriptive statistics. At every visit, adverse events and changes in medications will be registered.

Statistical Analysis Plan (per Diversigen, who performed computational analysis)

“To examine differences in abundance for taxa between treatment groups and across time, we examined taxa abundances at the Phylum, Family, Genus and ASV levels using the ASV count table as inputs. At each level of interest, count abundances were aggregated then transformed using the centered log ratio (CLR) transformation as implemented in the ALDEx2 R package. Briefly, transformation was performed using the `aldex.clr()` function, which estimates sequencing technical variation using Monte-Carlo sampling ($n = 128$) and generates CLR-transformed tables for each instance. A median CLR value for each taxon across all MC instances calculated and used for downstream plotting purposes.

Next, we performed differential abundance testing using LME models of the following model:

- `taxon_abundance ~ Treatment_Cohort*Timepoint + (1|SubjectID)`

Pairwise contrast p-values for all relevant Treatment_Cohort and Timepoint comparisons were extracted from the model using `emmeans()`. Next, p-values were corrected for multiple hypothesis correction across all taxa tested using the FDR method. Finally, all adjusted p-values generated by testing were averaged across all 128 MC instances to obtain a `padj` value for each taxon for each pairwise comparison of interest.

Using our standard significance thresholds of $padj < 0.05$, we found no taxa as significantly different in abundance at any level in any of the pairwise comparisons we examined. Therefore, we relaxed our threshold to $padj < 0.2$, which is less conservative but has been reported in the literature. Under this threshold, we found a few taxa that were significantly different.”

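### Does the missing Day 90 control swab leave the taxon model without a usable comparison with healthy skin at 3 months?

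*Combined protocol and SAP*

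**What the plan says.** Materials and Methods gives the control schedule as "Control Group will undergo skin swab at baseline and approximately 120 days later without any intervention". The Control Group visit table agrees: Visit 1 is Day 0, Visit 2 is Day 120 ± 5 days, and there is no Day 90 column. Both acne arms are swabbed at Day 0, Day 90 ± 5 and Day 120 ± 5.

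For the acne patients, "During the following 90 days, the Group will only be allowed to use either Altreno or BPO". After that visit the paths split: patients with significant improvement are asked to stop, and "If no significant improvement, they will be instructed to continue the therapy for additional 30 days". Pandemic clauses let visits slip. If control "subjects cannot return for 2nd visit in 120 days, the subjects will still remain in the study until able to do so"; for patients, "the subjects will either continue the therapy (or continue without therapy) and remain in the study until able to return".

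Data Analysis defines the primary outcome as change in the patients' own microbiome over three times, one of them "after 3 months of treatment". It then adds: "Comparisons of species diversity and relative abundance of the identified species will be made across healthy controls, Altreno group, and BPO group". No time point and no control reference swab are attached to that sentence. The next paragraph promises analysis of "three available microbial features (taxa, alpha diversity summary statistics, and community structure via beta diversity) across the three groups defined above".

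The Statistical Analysis Plan fits, for each taxon, a mixed model with cohort, timepoint, their interaction and a random subject intercept. It extracts those pairwise contrasts judged relevant. It does not define the levels of timepoint, list the contrasts or mention that controls have one swab fewer.

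**The concern.** Day 90 is the only post-baseline visit at which the protocol has every patient on assigned treatment; by Day 120 some have stopped and some have continued. A reader who wants to know whether treated skin resembles healthy skin would look there first, and there the controls have no swab.

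The unstated coding adds to the worry. With a day factor, the same-day contrast does not exist. With visit number, Visit 2 would pair the patients' Day 90 with the controls' Day 120 under one label. With day as a number, a control value at Day 90 would be interpolated on a straight line. Each reading gives a different 3-month comparison with controls, and if healthy skin changed over four months the possible references would carry different biases.

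**Working it through.** The plan gives no figure to reproduce, so the check is one of estimability, followed by a rough size for the choice of reference.

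**Inputs from the documents.** Controls at Days 0 and 120; each acne arm at Days 0, 90 and 120; up to 20 per group; full cohort-by-timepoint interaction.

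**Estimability.** Three cohorts by three times give 9 cells and 9 coefficients. Observed cells number 2 + 3 + 3 = 8.

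| Coding of timepoint | Columns | Rank | Patient-control comparison at 3 months |
|---|---|---|---|
| Day as a factor | 9 | 8 | No same-day contrast; Day 90 against control Day 0 or Day 120 is estimable |
| Visit number as a factor | 9 | 8 | Visit 2 contrast is estimable but sets patients' Day 90 against controls' Day 120; the empty cell is control Visit 3 |
| Day as a number | 6 | 6 | Estimable by linear interpolation |

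Under day-factor coding, 9 cells give 9 × 8 / 2 = 36 pairwise contrasts. The 8 that involve the empty cell are lost, leaving 28. Of the 3 × 3 = 9 same-day between-cohort contrasts, 7 remain; the two lost are Altreno-control and BPO-control at Day 90. Still estimable are every within-arm change, Altreno against BPO at all three days, both control contrasts at Day 0 and at Day 120, and all four cross-day contrasts (two arms at Day 90, each against either control swab). Change from Day 0 to Day 90 relative to controls is lost; change from Day 0 to Day 120 relative to controls is not.

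**Size of the reference choice.** Assume 20 per group, within-subject correlation ρ = 0.5, and a linear control drift of d SD from Day 0 to Day 120. Put weight w on the later control swab.

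- Standard error = √((1 + v)/20), with v = (1 − w)² + w² + 2w(1 − w)ρ.
- Bias of arm minus control, against the same-day target = (90 − 120w)/120 × d.

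The documents give no value for d. As an illustration, take the 95% half-width of the controls' own change: 2.093 × √(2 × 0.5/20) = 0.47 SD (0.55 at ρ = 0.3, 0.36 at ρ = 0.7).

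| Reference | w | SE (SD) | Bias | Bias at d = 0.47 |
|---|---|---|---|---|
| Control Day 0 | 0 | 0.316 | +3d/4 | +0.35 |
| Control Day 120 | 1 | 0.316 | −d/4 | −0.12 |
| Equal weights | 1/2 | 0.296 | +d/4 | +0.12 |
| 1/4 and 3/4 | 3/4 | 0.301 | 0 | 0 |

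**Does a weighted reference solve it?** Only on schedule. For an arm swab on day A and a later control swab on day T, the bias is A − wT days of drift. With w = 3/4 inside the ± 5 day windows, the worst case is 95 − 0.75 × 115 = 8.75 days, or 8.75/120 × 0.47 = 0.03 SD. If the control visit slips to Day 180, which the pandemic clause permits, it is 90 − 0.75 × 180 = −45 days, or −45/120 × 0.47 = −0.18 SD. Equal weights give 90 − 0.5 × 180 = 0 in that case. No fixed weighting is best throughout.

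**The case for a change.** The strongest case for acting is that it costs little. One sentence giving the coding and naming the control reference, or saying that there is none, would settle what a 3-month patient-control result means. No visit or swab is needed. Results are already reported, with nothing at an adjusted p below 0.05 and a few taxa at 0.2, and a reader cannot tell whether a Day 90 control contrast was among those tested. That untreated controls can be treated as stable is plausible but unstated, and their own change is known only to about ± 0.47 SD at ρ = 0.5.

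The opacity is real, and that part stands. It is missing detail, however, and does not show an analysis that fails. The sentence promising comparisons across the three groups can be met at Days 0 and 120 as it is written. Under day-factor coding the Day 90 contrast is simply absent. Mislabelling needs visit-number coding, and nothing shows that it was used.

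The bias figures are not evidence of harm, because 0.47 SD is a precision figure from an assumed sample size and correlation. The retained model, which pools within-subject error over 160 − 60 − 5 = 95 degrees of freedom at full recruitment, would give about 0.44.

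The 1/4–3/4 contrast relies on linear drift, which two control swabs cannot test. For controls it is also exactly what numeric day coding would produce. The plan corrects across taxa and describes no correction across contrasts, so each added contrast opens another uncorrected set of tests after a null result.

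**Conclusion.** No change to the plan. The control schedule does leave a gap at Day 90, but it touches only a non-randomised comparison that the plan does not explicitly call for. Leaving out a third control visit is a fair economy when controls are untreated and serve as a background reference. The patients-only primary comparisons and Altreno against BPO do not depend on it.

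The size is two of nine same-day contrasts under day-factor coding, with cross-day substitutes available for both arms. The possible bias from those substitutes cannot be stated without a drift figure, and the documents give none.

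Analysts can fill the unstated coding and contrast list sensibly, by labelling each reported contrast with the swab days it compares. That is a reporting matter of low weight. The weighted references exchange an open assumption of stability for an untestable one of linearity, and bring no clear gain.

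This conclusion assumes that the software does not report a value for a contrast that is not estimable, and that a visit-coded result, if there is one, is read against the visit tables. It concerns the taxon model only; the documents give no model for alpha or beta diversity from which the same check could be made.

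### The third primary state is one month after stopping, but only improvers stop at Day 90, and the stated model has no term separating on-drug from off-drug patients at Day 120

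*Combined protocol and SAP*

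**What the plan says.** **Visit rule (Materials and Methods, Experimental Group).** At Day 90 the next step depends on response: "If significant improvement, they will be asked to discontinue the therapy for 30 days". Otherwise, "If no significant improvement, they will be instructed to continue the therapy for additional 30 days". No threshold for improvement is given. Both kinds of patient then attend the same visit: "On the third visit (120 days +/- 5 days from the first visit), their acne will be scored, and repeat skin swab" is taken. A pandemic clause allows either state to run on: "the subjects will either continue the therapy (or continue without therapy) and remain in the study until able to return".

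**Primary outcome (Data Analysis, Primary Study Parameter(s)).** After baseline, the states to be compared are "2) after 3 months of treatment, and (3) 1 month 10 after discontinuation of treatment". The stray 10 looks like a page number picked up in text extraction. The groups are fixed in the next sentence: "Comparisons of species diversity and relative abundance of the identified species will be made across healthy controls, Altreno group, and BPO group". The section then sets out to analyse the "three available microbial features (taxa, alpha diversity summary statistics, and community structure via beta diversity) across the three groups defined above".

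**Model (Statistical Analysis Plan).** For taxa the model is "taxon_abundance ~ Treatment_Cohort*Timepoint + (1|SubjectID" (closing bracket dropped here). Pairwise contrasts are taken over cohort and timepoint. The levels of these two factors are not listed. No section adds treatment status, limits Day 120 to patients who stopped, or says how continuers are handled.

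**The concern.** One month after discontinuation is a state that only patients who stopped can be in. The Day-120 sample also holds patients with about four months of continuous treatment, and they differ from the stoppers in having responded less. A model indexed only by cohort and timepoint gives one Day-120 mean per arm, averaged over both kinds of patient.

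Three primary comparisons use that mean: Day 120 against Day 90 within an arm, Altreno against BPO at Day 120, and each arm against healthy controls, who are also swabbed at Day 120. A real rebound after stopping could be understated. Two drugs with the same recovery could look different because their stopping rates differ. A gap from healthy skin at Day 120 could reflect patients still on drug. Alpha and beta diversity are to be compared across the same three groups, so they inherit the problem, although the plan writes out a model only for taxa.

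**Working it through.** The plan gives no stopping share, standard deviation (SD), between-visit correlation or washout size, so there is no plan figure to reproduce.

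**Inputs from the documents:** up to 20 patients per arm, three swabs each, the Day-90 rule and the model formula.

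**Assumed:** stopping share *s*; washout shift δ (off-drug minus on-drug mean); for precision, total SD 1 and between-visit correlation 0.5.

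**1. Day-120 mean.** Pooled over status, the arm mean is *s*·μ_off + (1 − *s*)·μ_on. It equals μ_off only if *s* = 1 or μ_off = μ_on.

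**2. Day 90 to Day 120 within an arm.** If continuers do not change and response is unrelated to the shift, the contrast is *s*·δ + (1 − *s*)·0 = *s*·δ.

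| Assumed share stopping | Stoppers of 20 | Pooled contrast |
|---|---|---|
| 30% | 6 | 0.30 δ |
| 50% | 10 | 0.50 δ |
| 70% | 14 | 0.70 δ |
| 90% | 18 | 0.90 δ |

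Fitting the stated model to simulated data (20 per arm, true δ = 1, 200 runs per setting) gave 1.01 when all stop, 0.70 at 70% and 0.51 at 50%.

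**3. Altreno against BPO at Day 120.** With identical on- and off-drug states in both arms, the difference is (*s*_A − *s*_B)·δ. At 80% against 40% this is 0.40 δ, which comes only from the mix. The simulation gave 0.42.

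**4. Against healthy controls at Day 120.** The pooled contrast misses the off-drug contrast by (1 − *s*)(μ_on − μ_off) = −(1 − *s*)·δ, which is half the shift at 50% stopping.

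**5. Baseline to Day 90.** The point estimate does not use Day 120. The residual variance is shared, however, and mixing adds about *s*(1 − *s*)δ²/3 to it. With residual variance 0.5 and a 1 SD shift that fully reverses in stoppers:
- *s* = 0.5: √[(0.5 + 0.25/3)/0.5] = 1.08
- *s* = 0.3 or 0.7: √[(0.5 + 0.21/3)/0.5] = 1.07

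The standard error is therefore about 7–8% larger.

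**6. Within-stopper change.** At correlation 0.5 the SD of a change is √[2(1 − 0.5)] = 1. The 95% half-width in the mixed model is t(0.975, 72)/√n: 1.99/√10 = 0.63 SD with 10 stoppers and 1.99/√6 = 0.81 SD with 6. Both are before false discovery rate (FDR) correction across taxa.

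**7. Selection in that change.** Suppose there is no drug effect, but stopping correlates *r* with chance-affected Day-90 abundance. Stoppers then show a false rebound of 0.5·*r*·φ(z)/*s*, where z is the normal cut-off that gives stopping share *s*. For *r* from 0.3 to 0.7 this is 0.17–0.41 SD at 30% stopping, 0.12–0.28 SD at 50% and 0.07–0.17 SD at 70%.

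**The case against.** **Pooling is not stated.** The factor levels are undefined and only relevant contrasts were extracted, so the analyst may have coded treatment status or dropped continuers. The wording of the third state, on its face, covers only patients who stopped. The Statistical Analysis Plan is also a vendor's account in the past tense, while the protocol gives the analysis to the research team, so the formula may not be the whole analysis. This stands as a limit on certainty: a reader might infer that the analyst certainly pooled, and the documents do not show that. They do name three groups only and give no rule for continuers. If status was coded, one sentence saying so settles the matter.

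**The Day-120 arm comparison is randomised.** This also stands. A reader might infer that the contrast is invalid. It is a valid comparison of two regimens of the form: treat for 90 days, then stop if improved. Stopping rates are part of what each drug does. What it does not compare is the two drugs one month after stopping.

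**The size is unknown.** Also true. Every share above is an assumption, dilution is small if nearly everyone stopped, and the fractions change if continuers keep shifting in the extra 30 days.

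**Splitting by status selects responders.** It does, and it gives up precision. The split gets the label right; it does not remove selection.

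**Nothing passed the standard threshold.** No taxon reached an adjusted p below 0.05, so no washout finding at that level is being misattributed. A reader might instead infer that dilution produced the null. The documents cannot show this: the null is reported for every comparison examined, and dilution is at most one possible contributor at Day 120.

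**Conclusion.** The concern holds in a bounded form. The visit rule and the third primary state do not match, and the stated model and contrasts have nothing to reconcile them. Followed as written, Day-120 contrasts against Day 90, between arms and against healthy controls do not estimate the post-discontinuation state, unless nearly all patients stop or on- and off-drug states do not differ.

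The loss is the continuing share of any washout change, given unchanged continuers and response unrelated to the shift. Unequal stopping can add an arm difference of 0.40 of the shift at an assumed 80% against 40%. It does not follow that the whole primary analysis fails: baseline-to-Day-90 point estimates stand, with a modest loss of precision in the case worked above. The point should be fixed. Confidence is medium, because pooling is inferred and no stopping share is reported.

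**What to change.** Keep the treatment rule and change the analysis.

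1. Label each treated patient's Day-120 sample as stopped or continued from the visit-2 decision, checked against the visit-3 medication review. Report the number stopped per arm.
2. Report the after-discontinuation state only as the within-stopper Day-90-to-Day-120 change, with status interacting with timepoint within each arm. State that it applies to responders and is open to regression to the mean.
3. Report continuers as about four months on treatment.
4. Label any pooled Day-120 between-arm contrast as a regimen comparison, and any stopper-against-stopper comparison between arms as non-randomised.
5. Apply the same split to alpha diversity, beta diversity and the Day-120 comparison with healthy controls.

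Optionally, add a sensitivity model that splits only Day 120 and keeps a common Day-90 cell. It is not a safer default: if the drug shifts responders only, by 1 SD, its bias is −(1 − *s*) × 2/3, or −0.47, −0.33 and −0.20 SD at 30%, 50% and 70% stopping.

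The cost is a status label, a refit and relabelled tables, with no new visits or samples. The downside is a post hoc split and a washout estimate from fewer patients, in a responder subgroup that is not randomised.

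### The severity analysis leaves presence, dominance and the other taxa undefined, states no multiplicity correction for these tests, and gives PGA a chi-square test that needs categorised abundance and ignores the order of the grades

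*Combined protocol and SAP*

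**What the plan says.** The section Secondary Study Parameter(s) sets the aim: "The clinical severity will also be correlated to the presence and/or dominance of" P. acnes "and other populations using the following measures". Two measures follow.

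- PGA: "Categorical variable. A chi-square test will be performed for analysis".
- Leeds score: "A correlation analysis and depending on distribution, one-way ANOVA, a Kruskal Wallis or a Wilcoxon rank sum test will be performed for analysis".

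The section gives no cut-off for presence or dominance, no list or number of other taxa, no taxonomic level, no visit and no significance level. The visit schedule for the Experimental Group has both scores and the swabs at all three visits.

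Abundance is available as a quantity. Data Analysis plans this: "Comparisons of species diversity and relative abundance of the identified species will be made across healthy controls, Altreno group, and BPO group". The Statistical Analysis Plan computes centred log-ratio (CLR) values at four levels: phylum, family, genus and ASV.

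The Statistical Analysis Plan opens with its purpose, "To examine differences in abundance for taxa between treatment groups and across time", and says that "p-values were corrected for multiple hypothesis correction across all taxa tested using the FDR method". Its model has treatment cohort, timepoint, their interaction and a subject random effect. It has no severity term.

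**The concern.** There are two separate problems.

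**The form of the microbial variable.** A chi-square test needs categories on both axes, so for PGA the measured abundance has to be cut. With no cut-off fixed, it can be chosen after the data are seen. The test also treats the PGA grades as unordered, although a global severity grade is ordered. Both features cost power for P. acnes, the one organism the plan names.

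**The number of tests.** The same tests extend to taxa that are neither named nor counted, across two scores and possibly three visits, with no stated error control. The Statistical Analysis Plan reports that no taxon passed the 0.05 threshold in the abundance comparisons and that the threshold was then relaxed to 0.2. After a result like that, an open set of severity tests is a place where chance associations can surface and be read as findings.

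**Working it through.** The documents give no power or error-rate figure for this analysis, so there is nothing to reproduce. The calculations below only size the issue.

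**Inputs from the documents:** up to 40 acne patients; two scores; three visits; chi-square for PGA; a correlation and one of three group tests for Leeds.

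**Assumptions not in the documents:** all 40 patients contribute one observation at one visit; abundance and underlying severity are normal with correlation 0.45; PGA is that severity cut into four equally likely levels; two-sided 0.05 per test; 50–100 other taxa.

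**1. PGA (simulation, n = 40).**
- Chi-square, abundance split at its median against four PGA levels: about 40% power.
- Spearman, continuous abundance against the same four levels: about 76% power.

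**2. Leeds, only if a two-group test is relied on.** The efficiency of a split at quantile q relative to continuous abundance is φ(z_q)² / [q(1 − q)]. Multiplied by 40, it gives an effective sample size. Power is by simulation with Leeds treated as continuous.

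| Analysis | Relative efficiency | Effective n | Power |
|---|---|---|---|
| Spearman, continuous | – | 40 | about 81% |
| Rank-sum, median split | 0.637 | 25.5 | about 62% |
| Rank-sum, 80/20 split | 0.490 | 19.6 | about 48% |
| Rank-sum, 90/10 split | 0.342 | 13.7 | about 34% |

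The first row is an analysis that the plan already allows for Leeds.

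**3. Free choice of cut-off.** With no true association, taking the smallest p-value over five cut-offs (50th to 90th percentile) raises the false-positive rate for one taxon and one score from 5% to about 15% (simulation).

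**4. Number of tests, if no association exists.**
- P. acnes only, two scores at one visit: 1 − 0.95² = 9.8% chance of at least one false positive, taking the tests as independent.
- P. acnes only, two scores at three visits: 1 − 0.95⁶ = 26.5%, on the same basis.
- 50–100 other taxa × 2 scores = 100–200 tests per visit. Expected false positives are 100 × 0.05 = 5 to 200 × 0.05 = 10. This expected count does not need independence.

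**5. Does the FDR step reach these tests?** It adjusts p-values for contrasts between cohorts and timepoints, taken from a model with no severity term. The severity section does not refer to it. As written, it does not cover them.

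**The case against.** The strongest reply concerns Leeds. That sentence begins with a correlation analysis, which can use continuous abundance. A reader who looks only at "one-way ANOVA, a Kruskal Wallis or a Wilcoxon rank sum test will be performed for analysis" might infer that P. acnes is tested against both scores with its abundance cut up. The documents do not support that. They nowhere say that abundance is cut, and they do not say what the groups in the ANOVA or rank tests are. Those tests are often used for three or more groups, which need not be a present/absent or dominant/not split. This objection stands: the loss in step 2 is conditional. It does not help PGA, where chi-square is the only test named.

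A reader might also infer that an unlimited number of uncorrected tests was run. That goes too far as well. The number is unspecified, but it is bounded by the taxa detected, two scores and three visits. The plan is silent on correction; it does not rule correction out. No result of a severity analysis is reported, so it cannot be said that any conclusion has been distorted.

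Finally, this is a secondary association analysis in a study of up to 60 subjects with no stated confirmatory claim. That limits the weight of the point. It does not remove it, because the better method uses data already collected.

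**Conclusion.** The concern holds in limited form. What is certain from the text is that presence and dominance are undefined, the other taxa and the visit are open, no multiplicity correction is stated for the severity tests, and the PGA chi-square needs categorised abundance and ignores the order of the grades. For Leeds, information is lost only if the group tests on presence or dominance are preferred to the planned correlation, and the plan does not say which governs.

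The size for PGA is roughly 40% against 76% power, and for the other taxa 5–10 chance findings per visit. These figures are illustrative. They depend on the assumed correlation, PGA levels, taxon count and full recruitment, and the power comparison also depends on the median split. The change should be made; the point concerns a secondary analysis and does not bear on the primary comparison.

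**What to change.** - For both PGA and Leeds, use continuous CLR abundance with a rank correlation at one named visit. If all three visits are used, fit an ordinal or mixed model with a subject random effect instead.
- State which genus or ASVs represent P. acnes. The Statistical Analysis Plan works at phylum, family, genus and ASV level, with no species level.
- Make P. acnes the single named test per score.
- Put every other taxon-by-score test into one Benjamini-Hochberg family, labelled exploratory.
- Keep presence and dominance as description only.
- The Statistical Analysis Plan already reports abundance results, so new wording cannot restore prespecification. Label any severity analysis specified or completed after those results as post hoc, and report how many tests were done.

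The cost is revised wording and, for any severity analysis already completed, a rerun on existing data. No new samples or visits are needed. The downside is larger adjusted p-values for the other taxa.
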